#### **8.2.3.1. Temperature**

Temperature will be measured per local practice. The method chosen by the CRU should be used consistently throughout the study. No eating, drinking, or smoking is allowed for 15 minutes prior to the measurement.

### **8.2.4. Electrocardiograms**

Standard 12-lead ECGs utilizing limb leads (with a 10 second rhythm strip) should be collected at times specified in the [SoA](#) section of this protocol using an ECG machine that automatically calculates the heart rate and measures PR, QT, and QTc intervals and QRS complex. Alternative lead placement methodology using torso leads (eg, Mason-Likar) should not be used given the potential risk of discrepancies with ECGs acquired using standard limb lead placement. All scheduled ECGs should be performed after the participant has rested quietly for at least 5 minutes in a supine position.

To ensure safety of the participants, a qualified individual at the investigator site will make comparisons to baseline measurements. Additional ECG monitoring will occur if a) a post dose QTcF interval is increased by  $\geq 60$  msec from the baseline **and** is  $>450$  msec; or b) an absolute QT value is  $\geq 500$  msec for any scheduled ECG. If either of these conditions occurs, then 2 additional ECGs will be collected approximately 2 to 4 minutes apart to confirm the original measurement. If the QTc values from these repeated ECGs remain above the threshold value, then a single ECG must be repeated at least hourly until QTc values from 2 successive ECGs fall below the threshold value that triggered the repeat measurement.

If a) a post dose QTcF interval remains  $\geq 60$  msec from the baseline **and** is  $>450$  msec; or b) an absolute QT value is  $\geq 500$  msec for any scheduled ECG for greater than 4 hours or at the discretion of the investigator (or sooner, at the discretion of the investigator); or c) QTcF intervals get progressively longer, the participant should undergo continuous ECG monitoring. A cardiologist should be consulted if QTcF intervals do not return to less than the criteria listed above after 8 hours of monitoring (or sooner, at the discretion of the investigator).

In some cases, it may be appropriate to repeat abnormal ECGs to rule out improper lead placement as contributing to the ECG abnormality. It is important that leads be placed in the same positions each time in order to achieve precise ECG recordings. If a machine-read QTc value is prolonged, as defined above, repeat measurements may not be necessary if a qualified medical provider's interpretation determines that the QTcF values are in the acceptable range.

ECG values of potential clinical concern are listed in [Appendix 6](#).

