**Diagnostic Assessments:**

15. A positive urine drug test.
16. Screening supine BP  $\geq 140$  mm Hg (systolic) or  $\geq 90$  mm Hg (diastolic), following at least 5 minutes of supine rest. If BP is  $\geq 140$  mm Hg (systolic) or  $\geq 90$  mm Hg (diastolic), the BP should be repeated 2 more times and the average of the 3 BP values should be used to determine the participant's eligibility.
17. Screening PR  $> 100$  bpm or  $< 50$  bpm. If the PR is greater than 100 bpm or less than 50 bpm, the PR should be repeated 2 more times and the average of the three pulse rate values should be used to determine the participant's eligibility.
18. Baseline standard 12-lead ECG that demonstrates clinically relevant abnormalities that may affect participant safety or interpretation of study results (eg, baseline QTcF interval  $> 450$  msec, complete LBBB, signs of an acute or indeterminate-age myocardial infarction, ST-T interval changes suggestive of myocardial ischemia, second or third-degree AV block, or serious bradyarrhythmias or tachyarrhythmias). If the baseline uncorrected QT interval is  $> 450$  msec, this interval should be rate-corrected using the Fridericia method and the resulting QTcF should be used for decision making and reporting. If QTcF exceeds 450 msec, or QRS exceeds 120 msec, the ECG should be repeated 2 more times and the average of the 3 QTcF or QRS values should be used to determine the participant's eligibility. Computer-interpreted ECGs should be overread by a physician experienced in reading ECGs before excluding a participant.

19. Participants with **ANY** of the following abnormalities in clinical laboratory tests at screening, as assessed by the study-specific laboratory and confirmed by a single repeat test, if deemed necessary:

- AST **or** ALT level  $\geq 1.5 \times \text{ULN}$ ;
- Total bilirubin level  $\geq 1.5 \times \text{ULN}$ ; participants with a history of Gilbert's syndrome may have direct bilirubin measured and would be eligible for this study provided the direct bilirubin level is  $\leq \text{ULN}$ .
- Hemoglobin level  $\leq 120 \text{ g/L}$  ( $12.0 \text{ g/dL}$ );
- Platelet count  $\leq 150 \times 10^9/\text{L}$  ( $150,000 \text{ cells/mm}^3$ );
- WBC count of  $\leq 3.0 \times 10^9/\text{L}$  ( $3000 \text{ cells/mm}^3$ );
- ANC  $< 1500 \text{ cells/mm}^3$ ;
- ALC  $< 800 \text{ cells/mm}^3$ ;
- eGFR  $< 90 \text{ mL/min/1.73 m}^2$  based on the CKD-EPI 2009 equation;

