## 10.6. Appendix 6: ECG Findings of Potential Clinical Concern

ECG Findings That May Qualify as AEs

• Marked sinus bradycardia (rate <40 bpm) lasting minutes.

• New PR interval prolongation >280 msec.

• New prolongation of QTcF to >480 msec (absolute) or by <math>\geq 60</math> msec from baseline.

• New-onset atrial flutter or fibrillation, with controlled ventricular response rate: ie, rate <120 bpm.

• New-onset type I second-degree (Wenckebach) AV block of >30 seconds' duration.

• Frequent PVCs, triplets, or short intervals (<30 seconds) of consecutive ventricular complexes.

ECG Findings That May Qualify as SAEs

• QTcF prolongation >500 msec.

• New ST-T changes suggestive of myocardial ischemia.

• New-onset left bundle branch block (QRS >120 msec).

• New-onset right bundle branch block (QRS >120 msec).

• Symptomatic bradycardia.

• Asystole:

• In awake, symptom-free participants in sinus rhythm, with documented periods of asystole <math>\geq 3.0</math> seconds or any escape rate <40 bpm, or with an escape rhythm that is below the AV node.

• In awake, symptom-free participants with atrial fibrillation and bradycardia with 1 or more pauses of at least 5 seconds or longer.

• Atrial flutter or fibrillation, with rapid ventricular response rate: rapid = rate >120 bpm.

• Sustained supraventricular tachycardia (rate >120 bpm) (“sustained” = short duration with relevant symptoms or lasting >1 minute).

- Ventricular rhythms >30 seconds' duration, including idioventricular rhythm (heart rate <40 bpm), accelerated idioventricular rhythm (HR >40 bpm to <100 bpm), and monomorphic/polymorphic ventricular tachycardia (HR >100 bpm [such as torsades de pointes]).
- Type II second-degree (Mobitz II) AV block.
- Complete (third-degree) heart block.

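### Protocol 8.2.4 sets one repeat-ECG trigger on absolute QT but confirms and stops on QTc and refers on QTcF; read literally, some QTcF values of 501–509 msec require no repeat ECG

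*Protocol*

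**What the plan says.** Protocol 8.2.4 (Electrocardiograms) names a different interval at different steps of the same rule.

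- **Trigger for 2 additional ECGs.** Limb (a) is a QTcF rise of at least 60 msec from baseline together with a QTcF above 450 msec. Limb (b) applies if "an absolute QT value is" at least 500 msec. The continuous-monitoring sentence repeats both limbs and adds limb (c), progressive QTcF lengthening.
- **Confirmation.** "If the QTc values from these repeated ECGs remain above the threshold value", single ECGs follow at least hourly.
- **Stopping.** Hourly ECGs continue "until QTc values from 2 successive ECGs fall below the threshold value that triggered the repeat measurement".
- **Referral.** "A cardiologist should be consulted if QTcF intervals do not return to less than the criteria listed above after 8 hours of monitoring".
- **Later wording.** The paragraph on repeating abnormal ECGs begins "If a machine-read QTc value is prolonged, as defined above", as though the criteria above it were QTc criteria.

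Three other places bear on the point. Exclusion Criterion 18 (Protocol 5.2) says that when the uncorrected QT is long, "the resulting QTcF should be used for decision making and reporting". It also sets the baseline ceiling: "If QTcF exceeds 450 msec, or QRS exceeds 120 msec, the ECG should be repeated 2 more times", with the average deciding eligibility. Appendix 6 lists "QTcF prolongation >500 msec" among findings that may qualify as SAEs. The QTc tables in Protocol 9.3.4.1 and SAP 6.5.4 class a QTc above 500 msec as Severe.

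**The concern.** Limb (b) is worded on QT, but the section gives no stand-alone QTc or QTcF threshold to match it. Two things follow if the text is applied as written.

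First, QT and QTcF agree only at 60 bpm. Above that rate a QTcF over 500 msec can go with a QT under 500. If the rise from baseline is also below 60 msec, neither limb is met and no confirmatory ECG is mandatory, although Appendix 6 lists the value as a possible SAE.

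Second, after a limb (b) trigger it is unclear what must fall below 500. The 500 msec figure can be carried over to QTc, as the confirmation and stopping sentences suggest, or kept on QT, the variable that fired. The two readings can end the hourly ECGs at different points in the same participant.

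What is at stake is a participant-safety rule, not an estimate.

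**Working it through.** **Inputs**

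- Limb (a): QTcF rise ≥60 msec and QTcF >450 msec (Protocol 8.2.4).
- Limb (b), literal reading: QT ≥500 msec (Protocol 8.2.4).
- Highest eligible baseline QTcF: 450 msec (Criterion 18).
- Eligible screening pulse rate: 50–100 bpm (Criterion 17).
- Level of concern: QTcF >500 msec (Appendix 6).
- Correction: Fridericia, QTcF = QT × (HR/60)^(1/3), hence QT = QTcF × (60/HR)^(1/3).

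The plan states no figure of its own to reproduce here, so the rule is enumerated directly.

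**Step 1: when limb (a) is missed.** The rise must be 59 msec or less. With baseline at most 450:

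- QTcF 501 is missed from baselines 442–450 (rise 51–59).
- QTcF 505 is missed from baselines 446–450.
- QTcF 509 is missed from baseline 450 only.
- QTcF 510 is never missed, because 510 − 450 = 60.

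**Step 2: when limb (b) is also missed.** QT is below 500 when HR > 60 × (QTcF/500)^3.

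- QTcF 501: 60 × (501/500)^3 = 60.4 bpm.
- QTcF 509: 60 × (509/500)^3 = 63.3 bpm.

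**Step 3: an example.** At 70 bpm, take baseline 446 and post-dose QTcF 503. The rise is 57, so limb (a) is not met. QT = 503 × (60/70)^(1/3) = 478, so limb (b) is not met.

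**Step 4: grid.** Whole-msec pairs, baseline 380–450. These are grid cells, not probabilities. The middle column counts post-dose QTcF 501–599 with neither limb met. The last column counts post-dose QTcF 451–499 where literal limb (b) fires and limb (a) does not; these are the triggers that would be lost if QTcF simply replaced QT in limb (b).

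| HR (bpm) | Missed, QTcF above 500 | Lost by simple replacement |
|---|---|---|
| 50 | 0 | 725 (380 with QTcF above 480) |
| 55 | 0 | 245 (all above 480) |
| 58 | 0 | 65 (all above 480) |
| 60 | 0 | 0 |
| 61 | 17 | 0 |
| 62 | 35 | 0 |
| 63 | 44 | 0 |
| 64, 70, 80, 100 | 45 | 0 |

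Above 60 × (510/500)^3 = 63.7 bpm, QT ≥500 implies QTcF ≥510. That is a rise of at least 60 from any baseline of 450 or less, so at those rates literal limb (b) adds no trigger to limb (a).

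**Step 5: ambiguity in stopping.**

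- At 50 bpm, QT 500 gives QTcF 500 × (50/60)^(1/3) = 470.5, and QT 531 gives 499.7. Over QT 500–531 a QTc reading ends follow-up and a QT reading continues it.
- At 62 bpm, QT 499 gives QTcF 499 × (62/60)^(1/3) = 504.5. Here a QT reading stops and a QTc reading continues.

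**The case against.** The strongest reply is that limb (b) never says uncorrected. Where the protocol means that, it uses the word, as in Criterion 18. Elsewhere it uses absolute to contrast a value with a change from baseline: in the Appendix 6 entry on QTcF above 480 msec, and in the row labels of the QTc tables. Limbs (a) and (b) have the same change-and-value pairing. On that reading a letter was dropped, 500 msec is a QTc threshold, the missed band is empty, and confirmation, stopping and referral all line up. This is probably what was meant. It does not settle the text, because 8.2.4 itself lists QT and QTc as separate machine outputs and the QT wording appears in both sentences.

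A second reply is that a QTcF above 500 would not pass unseen. Appendix 6 flags it, ECGs are reviewed on an ongoing basis (Protocol 9.3.4), unplanned visits are allowed, AE follow-up is required as medically indicated (Appendix 3), and progressive lengthening leads to continuous monitoring. This stands as mitigation. These routes rest on judgement or recommendation, or come after the initial trigger; none makes a confirmatory ECG mandatory.

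Third, this is a single-dose study of about 12 people, so no later dose depends on the rule. That stands and keeps the severity low.

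A reader might also infer more than the documents support:

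- **That any baseline of 442–450 with a post-dose QTcF of 501–509 escapes.** Of the 9 × 9 = 81 whole-msec pairs, 36 rise by at least 60 msec and meet limb (a); from 442 to 509 is a rise of 67. The other 45 are missed only above the heart rates in Step 2, and none at 60 bpm or below.
- **That sites would diverge.** The protocol describes one CRU and states no second site. The ambiguity concerns how one team applies the rule.
- **That swapping QT for QTcF is clearly safer.** Step 4 shows that it removes literal triggers at slow heart rates, many with QTcF above 480, which Appendix 6 lists as a possible AE.

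**Conclusion.** The point holds as a low-severity wording defect in a safety rule. Read literally, a post-dose QTcF of 501–509 msec has no mandatory repeat ECG when the rise is 51–59 msec and heart rate exceeds about 60.4 to 63.3 bpm, depending on the value. Separately, the end of hourly ECGs after a limb (b) trigger is undefined at any heart rate other than 60 bpm; this part does not need a near-ceiling baseline.

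The documents do not support the claim that the sponsor intended an uncorrected trigger. The likely intent is QTc or QTcF, and that is a reason to correct the text.

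Assumptions: QTc means Fridericia, and baseline QTcF is at most 450. Criterion 18 may decide on an average of 3 ECGs, while SAP 3.4 takes the latest pre-dose value as baseline; an analysed baseline slightly above 450 would widen the band. The lower edge of 501 follows Appendix 6. No probability of occurrence is claimed, and the band is narrow for about 12 participants. No planned analysis changes.

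**What to change.** In both sentences of Protocol 8.2.4 (repeat ECGs and continuous monitoring), add an absolute QTcF of at least 500 msec as a trigger. In the confirmation and stopping sentences, name QTcF for the QTcF limbs. Keep QT of at least 500 msec as a separate limb, and confirm, stop and refer that limb on QT.

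If the sponsor states that QTcF alone was intended, the QT limb can be replaced instead. The sponsor should then accept that a QT of at least 500 msec with a QTcF below 500, which occurs below 60 bpm, no longer triggers by itself.

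With the added limb, the missed count is 0 at every heart rate and no existing trigger is lost. The cost is wording in one section and a few extra unscheduled ECGs in a participant whose QTcF reaches 500 msec. No scheduled procedure is added.

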### **8.2.5. Clinical Safety Laboratory Assessments**

See [Appendix 2](#) for the list of clinical safety laboratory tests to be performed and the [SoA](#) for the timing and frequency. All protocol required laboratory assessments, as defined in [Appendix 2](#), must be conducted in accordance with the laboratory manual and the [SoA](#). Unscheduled clinical laboratory measurements may be obtained at any time during the study to assess any perceived safety issues.

The investigator must review the laboratory report, document this review, and record any clinically relevant changes occurring during the study in the AE section of the CRF. Clinically significant abnormal laboratory findings are those which are not associated with the underlying disease, unless judged by the investigator to be more severe than expected for the participant's condition.

All laboratory tests with values considered clinically significantly abnormal during participation in the study or within Day 157 ( $\pm 3$  days) after the last dose of study intervention should be repeated until the values return to normal or baseline or are no longer considered clinically significant by the investigator or medical monitor.

If such values do not return to normal/baseline within a period of time judged reasonable by the investigator, the etiology should be identified and the sponsor notified.

See [Appendix 5](#) for suggested actions and follow-up assessments in the event of potential drug-induced liver injury.

All protocol required laboratory assessments, as defined in [Appendix 2](#), must be conducted in accordance with the laboratory manual and the [SoA](#).

If laboratory values from non protocol specified laboratory assessments performed at the institution's local laboratory require a change in participant management or are considered clinically significant by the investigator (eg, SAE or AE or dose modification), then the results must be recorded in the source data, and in the CRF AE narrative.

Participants may undergo random urine drug testing at the discretion of the investigator. Drug testing conducted prior to dosing must be negative for participants to receive study intervention.

### 8.2.5.1. HBV Testing

Participant's eligibility should be determined according to the following criteria based on the results of positive testing for HBsAg, HBcAb and HBsAb at screening.

- If all 3 tests are negative, the participant is eligible for study inclusion.
- If HBsAg is positive, the participant must be excluded from participation in the study.
- If HBsAg is negative, HBcAb is positive, and HBsAb is negative, the participant must be excluded from participation in the study.
- If HBsAg is negative, HBcAb is negative, HBsAb is positive, and prior HBV vaccination is unequivocally documented, the participant is eligible for the study and does not require HBV DNA monitoring during the study.
- If HBsAg is negative, HBcAb is negative, HBsAb is positive, and no unequivocal documentation of prior HBV vaccination is available, the participant is required to undergo HBV DNA reflex testing. If HBV DNA is detected, the participant must be excluded from participation in the study; If HBV DNA is undetectable, the participant is eligible for study inclusion but required to HBV DNA testing for the subsequent visits according to the [SoA](#).
- If HBsAg is negative, HBcAb is positive, and HBsAb is positive, the participant is required to undergo HBV DNA reflex testing. If HBV DNA is detected, the participant must be excluded from participation in the study; If HBV DNA is undetectable, the participant is eligible for study inclusion but required to HBV DNA testing for the subsequent visits according to the [SoA](#).

A participant who is tested viral load positive for HBV at screening will be excluded from the study. If there is any positive for viral load of HBV after screening, the participant should be discontinued from study treatment and referred to a hepatologist/specialist caring for HBV infection for appropriate evaluation and treatment.

### 8.2.6. Tuberculosis Test

Participants should be screened for TB using an IGRA per local guidelines. IGRA will be tested during screening or within 12 weeks prior to Day 1. The following are acceptable assays: QuantiFERON®-TB Gold In-Tube (QFT-GIT) test, T-SPOT®TB test, QuantiFERON®-TB Gold test (QFT-G) or QuantiFERON®-TB Gold Plus test (QFT-G Plus).. If T-SPOT test was completed within 12 weeks prior to Day 1, this is acceptable, however this test type cannot be offered for participants requiring the test during screening. If at any time the participant has signs or symptoms associated with TB, additional TB testing will be performed.

Participant's eligibility should be determined according to the following criteria based on the results of IGRA during screening or within 12 weeks prior to Day 1.

- Participants who test negative for IGRA is eligible for study inclusion.
- Participants who test positive for IGRA must be excluded from participation in the study.
- If the results of the IGRA are indeterminate, the test may be repeated, and if a negative result is obtained, enrollment may proceed. A positive test on repeat is exclusionary. Participants with repeat indeterminate IGRA results may be enrolled after consultation with an infectious disease and/or pulmonary specialist who determines that the risk of infection is low (ie, participant would be acceptable for immunosuppressant treatment without additional action).

Site personnel should follow the processing and analyses steps based on the assay chosen. Ensure incubation steps are followed as appropriate. Documentation of IGRA product used and the test result must be in the participant's source documentation.

#### **8.2.7. Viral Surveillance**

Blood samples for possible analysis of CMV, EBV, HSV-1, HSV-2, VZV and HHV6 will be collected according to the times outlined in the [SoA](#).

*Note: Due to long turnaround time, the retrospective nature of these labs might make their reporting time quite delayed.*

In addition to time points specified, a blood sample for viral surveillance sample may also be taken at the time of an AE, as clinically appropriate.

#### **8.2.8. COVID-19 Specific Assessments**

Participants will be tested for SARS-COVID-19 infection by PCR at the timepoints specified in the [SoA](#), or if they develop COVID-19 like symptoms. Additional testing may be required by local regulations or by the Principal Investigator. The test result must be negative in order for a participant to proceed with admission on Day -1. COVID-19 tests may be conducted at a central or local laboratory. COVID-19 specific assessments data will be considered source data. If the participant has a positive COVID-19 test result, the concerned participant may be isolated and withdrawn from the study at the discretion of the investigator upon consultation with the sponsor. The positive COVID-19 test result should be recorded in the AE section of the CRF.

#### **8.2.9. Pregnancy Testing**

Pregnancy tests may be urine or serum tests, but must have a sensitivity of at least 25 mIU/mL. Pregnancy tests will be performed in WOCBP at the times listed in the [SoA](#). Following a negative pregnancy test result at screening, appropriate contraception must be commenced and a second negative pregnancy test result will be required at the baseline visit

prior the participant's receiving the study intervention. Pregnancy tests will also be done whenever 1 menstrual cycle is missed during the active treatment period (or when potential pregnancy is otherwise suspected) and at the end of the study. Pregnancy tests may also be repeated if requested by IRBs/ ECs or if required by local regulations. If a urine test cannot be confirmed as negative (eg, an ambiguous result), a serum pregnancy test is required. In such cases, the participant must be excluded if the serum pregnancy result is positive.

#### **8.2.10. Infusion Site Assessment**

Infusion site reactions will be assessed according to the [SoA](#). Infusion site reactions may include but are not limited to: erythema, induration, ecchymosis, pain, and pruritus.

Any signs or symptoms related to either an infusion site reaction should be treated according to the investigator's standard of care and reported as adverse events.

